8.5 Adjustments for Multiplicity

As this is an exploratory study with no primary or secondary endpoints, there will be no multiplicity adjustments and all analyses are considered hypothesis-generating.

9. Disposition of Subjects

Subject disposition will be presented in terms of the numbers and percentages of subjects who were randomized to masked study drug, with subcategories of dosed with the masked study drug and did not dose with masked study drug; who were included in the ITT and Safety Populations; and who completed the study and discontinued from the study. Subjects who are not discontinued from the study will be considered study completers. Disposition will be summarized by treatment group and overall for all subjects. Percentages will be calculated using screened subjects as the denominator unless otherwise specified.

The reasons for premature study discontinuation will be summarized by treatment group and overall for all discontinued subjects. Percentages will be calculated using discontinued subjects as the denominator. The reasons for study discontinuation that will be summarized include: lost to follow-up, adverse event (AE),

protocol violation, administrative reasons, sponsor termination of study, subject request/withdrawal, and other. A subject listing will be provided that includes the date of and reason for premature study discontinuation.

The number and percentage of subjects with any deviation will be summarized by treatment group and overall for all subjects. The protocol deviations that will be summarized include the following categories: non-compliance with informed consent, non-compliance with study inclusion or exclusion criteria, site's non-compliance with study treatment, improper protocol procedures at site, site's failure to report serious adverse events (SAE) and/or adverse events (AE), non-compliance with any scheduled study visit, use of disallowed concomitant medications, subject's failure to follow instructions, and other. A subject listing will be provided that includes the date of the deviation, the deviation category, the deviation description, and the classification of whether the deviation was judged to be major or minor in a masked review.

Details of the study randomization, including randomization date, randomized treatment, and actual treatment, will also be included within a subject listing.

10. Demographics and Physical Examination

10.1 Demographic Variables

The demographic variables collected in this study include age, gender assigned at birth (i.e., sex), race, ethnicity, and iris color. Subjects who record more than one race will be grouped into a single category denoted as Multi-racial in the summary table and will be reported as collected in the subject listing. Iris color will be summarized at the subject level. Demographic variables will be summarized for the ITT and Safety Populations, separately.

Age (years) will be summarized, by treatment group and overall for all subjects, using continuous descriptive statistics. Age will be reported in years and calculated using the following formula:

Age (years) = (Informed Consent Date – Date of Birth) / 365.25, truncated as an integer

The number and percentage of subjects will be presented, by treatment group and overall for all subjects, for sex, race, ethnicity, and iris color.

A subject listing that includes all demographic variables will be provided.

10.2 Physical Examination

Physical examinations of general health, head, eye, ear, nose and throat (HEENT), and other body systems will be graded as normal, abnormal not clinically significant (NCS), or abnormal clinically significant (CS).

A subject listing that includes all physical examination results will be provided.

11. Medical History and Concomitant Medications

Listings of medical history, concomitant medications, and concomitant procedures will be generated separately, as well as separately for ocular and non-ocular data.

11.1 Medical History

Medical history will be coded using the Medical Dictionary for Regulatory Activities (MedDRA), Version 26.1

Non-ocular medical history will be summarized using discrete summary statistics and presented by treatment group and overall for all subjects at the subject level by System Organ Class (SOC) and Preferred Term (PT) using the Safety Population. Ocular medical history will be similarly summarized at the subject level. If a subject reports the same PT multiple times within the same SOC, that PT will only be reported once within that SOC. As with the PT, if a subject reports multiple conditions within the same SOC, that SOC will only be reported once. In the summaries, SOCs are ordered in ascending alphabetical order, and PTs within an SOC are sorted by descending frequency for all subjects.

11.2 Prior and Concomitant Medications

Prior and concomitant medications will be coded using the World Health Organization Drug Dictionary (WHODrug) Global, B3, September 2023 version and summarized to the therapeutic drug class (Anatomical Therapeutic Chemical [ATC] 4 classification) and preferred name. If the ATC 4 classification is not provided, then the next highest classification that is provided in the coding dictionary will be used. The preferred name will be defined as the active ingredient; if the active ingredient is not provided or includes more than two ingredients (e.g., multivitamins), then the drug name will be summarized as the preferred name.

Concomitant medications are defined as those medications listed as having been taken (1) prior to initiation of study drug administration and continuing for any period of time following the first administration of study drug or (2) at any time following the first administration of study drug. Prior medications are defined as those medications that are stopped prior to initiation of study drug administration.

Concomitant medications will be summarized using the ITT Population. Medications will be tabulated for each treatment group using frequencies and percentages. Subjects may have more than one medication per ATC text. At each level of subject summarization, a subject will be counted once if he/she reports one or more medications. Percentages will be based on the number of subjects in each treatment group. In the summaries, ATC Classes and preferred names will be presented in ascending alphabetical order. A listing will be provided of prior and concomitant medications.

11.3 Concomitant Procedures

Concomitant procedures will be coded using the Medical Dictionary for Regulatory Activities (MedDRA), Version 26. 1. Concomitant procedures will not be summarized, but a listing will be provided.

12. Dosing Compliance and Treatment Exposure

In addition to the analyses described in the following sections, subject listings will be provided for study drug assignment, study drug instillation, and subject daily dosing diary records.

12.1 Dosing Compliance

Dosing compliance (% compliance) will be assessed by calculating the number of actual doses received and comparing that to the number of expected doses as follows:

The number of actual doses received will be calculated from the number of used vials recorded in the drug accountability eCRF or from the subject diary and in-office instillations. The number of expected doses that will be used for calculating compliance will be calculated as:

for all subjects, regardless of study completion status.

A categorical dosing compliance variable will also be derived as non-compliant (< 80%), compliant (≥ 80% and ≤ 125%), and over compliant (> 125%).

Dosing compliance (%) will be summarized with continuous descriptive statistics for each treatment group using the ITT Population. The compliance category defined above will be summarized with discrete summary statistics.

A subject listing of dosing compliance will also be produced.

12.2 Treatment Exposure

Extent of treatment exposure for completed or discontinued subjects will be calculated in days using the following:

Extent of treatment exposure for subjects who were lost to follow-up will be calculated in days using the following:

Extent of treatment exposure for each subject exposed to study drug will be summarized with continuous descriptive statistics for each treatment group using the Safety Population. A subject listing of treatment exposure will also be produced.

13. Exploratory Efficacy Analyses

13.1 Primary Analysis of Exploratory Efficacy Variables

All efficacy analyses will be conducted using the ITT Population.

13.1.1 FLUORESCEIN STAINING (ORA CALIBRA® SCALE)

Fluorescein staining will be conducted at Visits 3, 4 (pre-CAE, post-CAE, and pre- to post-CAE), and 5 (pre-CAE, post-CAE, and pre- to post-CAE) in the following regions: central, superior, inferior, temporal, nasal, corneal sum, conjunctival sum, and total eye score.

The staining will be graded with the Ora Calibra[®] Corneal and Conjunctival Staining Scale, which is as follows: 0 = None, 1 = Trace, 2 = Mild, 3 = Moderate, 4 = Severe. Half (0.5) increments may be used.

The fluorescein staining results for the study eye will be summarized using continuous descriptive statistics by visit and eye for each treatment group and all randomized subjects. A subject listing of fluorescein staining results will also be produced.

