10.4 STATISTICAL ANALYSIS

10.4.1 General Considerations

Continuous variables will be summarized descriptively using number of subjects (n), mean, standard deviation, median, minimum, and maximum. Categorical variables will be summarized using counts and percentages.

All summaries will be presented by treatment group. Summaries will be provided for demographics, baseline medical history, concurrent therapies, and subject disposition.

For the purpose of summarization, medical history, concurrent therapies, and AEs will be coded to Medical Dictionary for Regulatory Authorities (MedDRA) MedDRA and World Health Organization (WHO) Drug dictionaries, as appropriate.

Baseline measures are defined as the last non-missing measure prior to the initiation of randomized study treatment, usually at Visit 2. Change from baseline will be calculated as follow-up visit value minus baseline value. Treatment comparisons between active and vehicle will be calculated as active minus vehicle.

All analyses will be 2-sided at a significance level of 0.05 unless otherwise specified. For all efficacy analyses, 95% confidence intervals on the difference between each dose of IC265 and vehicle will be provided.

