| MedDRA | Medical Dictionary for Regulatory Activities |
| MI | Multiple Imputation |
| NCS | Not Clinically Significant |
| QD | Quaque die (Once Daily) |
| PDF | Portable Document Format |
| PP | Per Protocol |
| PT | Preferred Term |
| RDC | Remote Data Capture |
| RTF | Rich Text Format |
| SAE | Serious Adverse Event |
| SAP | Statistical Analysis Plan |
| SD | Standard Deviation |
| SDC | Statistics & Data Corporation |
| SDTM | Study Data Tabulation Model |
| SOC | System Organ Class |
| TEAE | Treatment-Emergent Adverse Event |
| VA | Visual Acuity |
| WHODrug | World Health Organization Drug Dictionary |

1. Introduction

The purpose of this statistical analysis plan (SAP) is to describe in detail the planned analyses and reporting for protocol 23-110-0002, Version 3.0 dated 22AUG2023. The statistical analysis methods presented in this document will supersede the statistical analysis methods described in the clinical protocol. If additional analyses are required to supplement the planned analyses described in this SAP, they may be completed and will be identified in the clinical study report.

This SAP is being written with due consideration of the recommendations outlined in the most recent International Conference on Harmonisation (ICH) E9 Guideline entitled Guidance for Industry: Statistical Principles for Clinical Trials and the most recent ICH E3 Guideline entitled Guidance for Industry: Structure and Content of Clinical Study Reports.

The decision to terminate protocol 23-110-0002 was determined 16NOV2023 due to the emergent adverse events of Epithelial Haziness. Details on how the termination affected the protocol-state analyses can be found in Section 17.

2. Study Objectives

The objective of this study is to compare the safety and efficacy of IC265 Ophthalmic Solution 1% to placebo for the treatment of the signs and symptoms of dry eye disease.

3. Study Endpoints

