3.5 Statistical Hypotheses

The clinical hypotheses for this study is that IC265 Ophthalmic Solution 1% twice daily (BID) is superior to its vehicle (BID) for the efficacy endpoints.

4. Study Design and Procedures

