8.1 Unit of Analysis

Safety endpoints will be analyzed for both eyes. For efficacy endpoints, the unit of analysis will be the study eye, or the "worst eye," as defined by the following:

Study Eye: Eyes are eligible for analysis if they meet all of the inclusion criteria. In the case that both eyes are eligible for analysis, the study eye will be the eye with the worst (higher) total corneal fluorescein staining, based on the sum of the inferior, superior, and central regions, at baseline (Visit 2) pre-CAE. If the total corneal staining is the same in both eyes, then the right eye will be selected as the study eye.

The non-study eye will be referred to as the fellow eye. Fellow eye safety summaries will also be presented as appropriate. Additionally, non-ocular AEs and medical history will be presented at the subject level.

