13.1.6 OCULAR SURFACE DISEASE INDEX (OSDI)

Ocular Surface Disease Index (OSDI[©]) includes the following questions:

- 1. Eyes that are sensitive to light?
- 2. Eyes that feel gritty?
- 3. Painful or sore eyes?
- 4. Blurred vision?
- 5. Poor vision?
- 6. Reading?
- 7. Driving at night?
- 8. Working with a computer or bank machine (ATM)?
- 9. Watching TV?
- 10. Windy conditions?
- 11. Places or areas with low humidity (very dry)?
- 12. Areas that are air conditioned?

OSDI[©] will be collected for both eyes at Visits 1, 2, 3, 4 and 5 (pre-CAE). The 5-unit scale for responses to the OSDI[©] is given by the following: 0 = None of the time, 1 = Some of the time, 2 = Half of the time, 3 = Most of the time, and 4 = All of the time. The total OSDI[©] score is calculated by the following:

Note that the number of questions answered in the denominator should exclude those questions with a response of "N/A." Continuous descriptive statistics, including 95% CIs, as well as changes from baseline will be summarized by treatment group as well as between treatment groups. All categorical safety assessments will be summarized by treatment and time point (as applicable) using discrete summary statistics. A subject listing of OSDI® results will also be produced.

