15.2 Visual Analog Scale

A VAS instrument measures a characteristic that spans a continuum, cannot be precisely or optimally measured by, or would lack sensitivity in distinguishing subtle changes on an ordinal scale. VAS will be administered to assess the subject's experience of ocular discomfort (unrelated to study drug instillation), where higher score indicates greater discomfort.

A subject listing that includes all VAS results will be provided.

16. Interim Analyses

There will be no interim analyses in this study. To note, the study was terminated early on 16NOV2023.

17. Changes from Protocol-Stated Analyses

Changes from the protocol-stated analyses, due to early termination of the study on 16NOV2023, include the following:

- Per Protocol population will not be determined.
- No imputation will be used for efficacy or safety endpoints. Specifically, the ITT population will not be analyzed using the Last Observation Carried Forward (LOCF) imputation method and multiple imputation.
- Sensitivity analyses will not be conducted as the PP population has been removed and no imputation will be used.
- Statistical testing will not be conducted. Descriptive statistics will be utilized for the efficacy and safety endpoints.

18. References

- ICH Harmonised Tripartite Guideline: Statistical Principles for Clinical Trials E9. International Council for Harmonisation of Technical Requirements for Pharmaceuticals for Human Use. 05 February 1998.
- 2. *ICH Harmonised Tripartite Guideline: Structure and Content of Clinical Study Reports E3*. International Council for Harmonisation of Technical Requirements for Pharmaceuticals for Human Use. 30 November 1995.

19. Revision History

Documentation of revision to the SAP will commence after approval of the final version 1.0.

20. Tables

Tables that will be included in the topline delivery are shown in boldface font.

| Table Number | Title | Population |
|--------------|---|-------------------------------|
| 14.1.1 | Subject Disposition | All Screened Subjects |
| 14.1.2 | Protocol Deviations | Intent-to-Treat Population |
| 14.1.2.1 | Demographics | Intent-to-Treat Population |
| 14.1.2.2 | Demographics | Safety Population |
| 14.1.3.1 | Ocular Medical History | Safety Population |
| 14.1.3.2 | Non-Ocular Medical History | Safety Population |
| 14.1.4.1 | Ocular Concomitant Medications | Intent-to-Treat Population |
| 14.1.4.2 | Non-Ocular Concomitant Medications | Intent-to-Treat Population |

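### Only OSDI has a planned IC265-versus-placebo summary with 95% CIs; for the other eight efficacy endpoints the SAP plans no effect estimate and no precision

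*SAP*

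**What the plan says.** - **Aim.** SAP section 2 states: "The objective of this study is to compare the safety and efficacy of IC265 Ophthalmic Solution 1% to placebo". SAP 3.5 keeps the hypothesis that IC265 "is superior to its vehicle (BID) for the efficacy endpoints". SAP 3.3 lists nine efficacy endpoints; the redness entry includes mean change from Visit 2 to Visit 5, both pre-CAE.
- **What a summary contains.** SAP 8.4 defines continuous summaries as n, mean, SD, median, minimum and maximum. It fixes the sign of a treatment difference as active minus placebo, but attaches that to no endpoint and to no interval.
- **Eight endpoints.** For fluorescein staining, SAP 13.1.1 says: "The fluorescein staining results for the study eye will be summarized using continuous descriptive statistics by visit and eye for each treatment group". Sections 13.1.2-13.1.5 and 13.1.7-13.1.9 vary in detail: some add a pooled column of actively treated subjects, and some omit the by-eye split. None asks for a between-arm difference, an interval or a change from baseline.
- **One endpoint.** For OSDI, SAP 13.1.6 says: "Continuous descriptive statistics, including 95% CIs, as well as changes from baseline will be summarized by treatment group as well as between treatment groups".
- **Declared changes.** SAP 17 drops the per-protocol population, imputation, sensitivity analyses and testing: "Statistical testing will not be conducted. Descriptive statistics will be utilized for the efficacy and safety endpoints". It does not mention confidence intervals.
- **Protocol Version 1.0, section 10.4.1.** "For all efficacy analyses, 95% confidence intervals on the difference between each dose of IC265 and vehicle will be provided". SAP section 1 adds: "The statistical analysis methods presented in this document will supersede the statistical analysis methods described in the clinical protocol".
- **Selection.** Protocol 5.3 requires thresholds on symptoms, Schirmer, redness, fluorescein and lissamine staining and CAE response, at Visits 1 and 2. If both eyes qualify, SAP 8.1 says "the study eye will be the eye with the worst (higher) total corneal fluorescein staining", judged at Visit 2 pre-CAE. SAP 8.3 makes Visit 2 the usual baseline.

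**The concern.** A comparative objective needs a contrast between arms and a statement of how well that contrast is known. For eight endpoints the planned output is two separate columns of arm statistics, so the reader gets neither.

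The design makes this matter more. Eyes qualify on Visit 2 values, and those values also serve as baseline. Measures with an entry threshold are then expected to drift back toward their usual level in both arms, with no drug effect. For staining, redness, symptoms and CAE response that looks like improvement. For Schirmer, which has a 10 mm upper limit at entry, the drift is upward, which also looks like improvement. The concurrent contrast removes this drift; a within-arm change does not. TFBUT and the diary score have no entry threshold of their own, so for them the argument rests on the comparative objective alone.

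**Working it through.** **1. Text comparison.** There is no planned power or effect size to reproduce: Protocol 10.3 and SAP 5 say that no sample size calculation was done.

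| Efficacy endpoint | SAP section | Between-arm summary | 95% CI | Change from baseline |
|---|---|---|---|---|
| Fluorescein staining | 13.1.1 | no | no | no |
| Discomfort and symptoms | 13.1.2 | no | no | no |
| Lissamine green staining | 13.1.3 | no | no | no |
| TFBUT | 13.1.4 | no | no | no |
| Redness | 13.1.5 | no | no | no, although 3.3 names it as an endpoint |
| OSDI | 13.1.6 | yes | yes | yes |
| Schirmer | 13.1.7 | no | no | no |
| Discomfort during CAE | 13.1.8 | no | no | no |
| Diary score | 13.1.9 | no | no | no |

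Safety sections 14.2 (visual acuity) and 14.5 (IOP) do specify change from baseline, so the SAP asks for it where it wants it.

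**2. Precision of the missing contrast.** For equal arms of n and a common SD, the half-width in SD units is t(0.975, 2n-2) × √(2/n).
- n = 20: 2.024 × 0.316 = 0.64
- n = 15: 2.048 × 0.365 = 0.75
- n = 10: 2.101 × 0.447 = 0.94

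The plan was about 20 per arm. The number reached at termination is not given, so this is a range.

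**3. Drift without drug effect (simulation, assumed inputs).** The documents give no staining distribution. Assumed: regional score mean 1.3, SD 0.8; mean CAE rise 0.6, SD 0.6; visit-to-visit reliability 0.4 to 0.8; true regional variance split 50% subject, 20% eye, 30% region; half-point grading from 0 to 4; no treatment effect; 600,000 screened subjects per setting. Rules applied at Visits 1 and 2: one corneal region at least 2, corneal sum at least 4, inferior CAE rise at least 1, all in the same eye. The worse Visit 2 eye was then chosen. The redness, lissamine, Schirmer and discomfort criteria were not modelled.

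| Quantity, Visit 2 to follow-up | Reliability 0.8 | Reliability 0.4 |
|---|---|---|
| Pre-CAE corneal sum, without the CAE-response criterion | -0.20 | -0.56 |
| Pre-CAE corneal sum, all modelled criteria | +0.01 | -0.14 |
| Inferior CAE rise, all modelled criteria | 1.38 to 1.09 (-0.29) | 1.52 to 0.82 (-0.70) |
| Post-CAE inferior staining, all modelled criteria | -0.20 | -0.50 |

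The CAE-response criterion favours eyes with a low pre-CAE inferior reading, and this nearly cancels the fall in the pre-CAE sum. Other assumed inputs (corneal-sum mean 4 to 5, SD 2, between-eye correlation 0.7, reliability 0.8 or 0.5) give falls in the sum of up to about 0.29 with that criterion included. For the inferior CAE rise, an assumed mean of 1 and SD of 0.8 gives a shrinkage of 0.1 to 0.3.

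**4. What the contrast does.** With arms of 20 and no effect, the between-arm contrast in corneal-sum change excluded zero in 4.7% to 5.5% of trials in every setting, close to the nominal 5%. Within one arm, without the CAE-response criterion, the 95% CI lay wholly on the improvement side in 15% to 39% of arms. With all modelled criteria it did so in 2% to 6%, against a nominal 2.5%.

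**The case against.** **The SAP went descriptive openly, after a safety termination.** True, and the decision to drop testing is not in dispute. But an interval on a difference is an estimate, and the same SAP keeps intervals for OSDI, so its own idea of descriptive does not exclude them.

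**OSDI may be the anomaly.** Section 13.1.6 contains a sentence on categorical safety assessments, which suggests pasted text, and it never spells out an IC265-minus-placebo difference. This is fair. Even so, the SAP is then inconsistent within itself, and deleting the OSDI contrast would leave the comparative objective with no estimate at all.

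**A reader might infer that the comparison cannot be made.** The documents do not support that. Both arms are tabulated with n, mean and SD, and 8.4 fixes the sign, so a crude difference can be derived. For change from baseline only the difference in means can be obtained this way, because the SD of change is not tabulated.

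**A reader might infer an undisclosed departure from the protocol.** This cannot be shown. The SAP was written for protocol Version 3.0 of 22 August 2023; only Version 1.0 of 12 June 2023 is available, and the sentence in 10.4.1 may have changed.

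**A reader might infer a large spurious fall in corneal staining.** A model with only the severity thresholds and worse-eye choice suggests 0.20 to 0.56 points, or 0.35 to 0.80 under other inputs. That omits inclusion criteria 11a and 12, which bring it close to zero. Nor does the SAP anywhere treat within-arm change as evidence: it calls all analyses hypothesis-generating, and the placebo column would show any shared drift.

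**Many intervals would be read as tests.** This stands as a cost. The two stains alone could produce up to 2 stains × 8 regions × 3 visits × 3 time points = 144 intervals, of which 0.05 × 144 ≈ 7 would be expected to exclude zero with no effect.

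**Conclusion.** The point holds as a gap between objective and output. One of nine efficacy endpoints has a planned between-arm summary with 95% CIs; the other eight have neither an effect estimate nor its precision, and redness also lacks the change from baseline named in 3.3. This rests on the SAP text alone and does not depend on the protocol version.

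The selection argument supports the point but is smaller and less uniform than it first appears. It applies to measures with an entry threshold. Under the assumed inputs it is modest to sizeable for the inferior CAE rise (a shrinkage of about 0.1 to 0.7 points) and small for the pre-CAE corneal sum (about +0.01 to -0.3). Those sizes are illustrations, since no reliability or distribution is documented.

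The contrast would be imprecise, with half-widths of roughly two-thirds of an SD to nearly one SD. In a truncated trial that imprecision is itself worth reporting. The gap should be corrected, but it does not invalidate the study.

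**What to change.** In SAP 13.1.1-13.1.5 and 13.1.7-13.1.9, and in Tables 14.2.1.1-14.2.1.6, 14.2.1.8 and 14.2.1.9, add at each post-baseline visit and time point (for the diary, each post-baseline window) the IC265-minus-placebo difference with a 95% CI. Use the difference in mean change from baseline where a baseline exists, including redness. Label the intervals descriptive, unadjusted for multiplicity and without p-values.

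Add one sentence saying that within-arm change is not evidence of effect, because eyes were selected on values that also serve as baseline. In SAP 17, state whether the intervals in protocol 10.4.1 are kept or dropped, checked against protocol Version 3.0. If the sponsor prefers not to add the contrasts, SAP 17 should say so, and 13.1.6 should be brought into line.

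The cost is SAP wording and extra columns in eight tables, from data already collected. The downside is many wide intervals, which some readers may treat as informal tests; the labelling limits that but does not remove it.
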